9.2. Availability

^{177}Lu -PSMA-617 (IND# 131966) and ^{68}Ga -PSMA-HBED-CC (IND# 124495) are investigational agents supplied to investigators by Weill Cornell Medicine.

9.3. Agent Ordering

Upon enrollment of the subject, the WCM Study Coordinator will be notified about the ^{177}Lu -PSMA-617 and ^{68}Ga -PSMA-HBED-CC infusion dates. The WCM Study Coordinator will arrange with the staff of Nuclear Medicine Division at WCM for the timely labeling and delivery of the radiolabeled PSMA peptides to the site of infusion.

The dates for study visits will be confirmed with the subject, site of infusion, and site of imaging.

9.4. Agent Accountability

The investigator, or a responsible party designated by the investigator, will maintain a careful record of the inventory and disposition of all agents received from Sponsor on a Drug Accountability Record Form (DARF).

9. CORRELATIVE/SPECIAL STUDIES

9.1 Laboratory Correlative Studies

9.1.1. Cell-Free Plasma DNA:

Peripheral blood will be collected in two 10 mL Cell-Free DNA BCT[®] tubes (Streck) at the specified time points (Screening and EOS visit) and processed per the lab manual. These samples are collected for research purposes only and will not be billed to the subject. The cell-free plasma DNA will be analyzed for genomic studies and to identify DNA repair alterations.

9.1.2. Archival tissue:

Archival tissue will be requested during the screening visit. Unstained slides containing tumor material from archival paraffin-embedded tissue should be obtained per the lab manual. If available, metastatic tissue is preferred to prostate biopsy/prostatectomy specimens. The tissue will be analyzed for PSMA expression, DNA repair pathways, and other genomic analyses for research purposes only.

9.1.4 Immune assays

Serum samples will be obtained during screening prior to treatment and at the main efficacy visit for immune biomarkers and processed as per the lab manual. CTC collection for calreticulin expression analysis will be collected during screening or on D1 prior to treatment and at the D85 scan visit and processed as per the lab manual. CTCs for immune analysis will be collected at the WCM site only. Results of these assays will not be billed to the patient and are for research purposes only.

9.2. Imaging Studies

Imaging studies (including ^{68}Ga -PSMA-HBED-CC PET/CT and ^{177}Lu -PSMA-617 Planar/SPECT Imaging) will be performed as described in schedule as well as clinically indicated to assess disease response. In subjects enrolled in this study, the measurable disease response will be calculated using Response Evaluation Criteria in Solid Tumors (RECIST Version 1.1) with PCWG3 modifications.

Consenting subjects will undergo an optional study involving two scans with ^{68}Ga -PSMA-HBED-CC (with a minimum of 6 h and maximum of 2 days between the two injections). This cohort of patients will be analyzed to ensure that the peak standardized uptake values (including SUV_{mean} , SUV_{max} , SUV_{peak} (SUV_{peak} not applicable to brain) of the lesions in the same patient/lesion is within an acceptable range of repeatability (+/- 30%) as demonstrated by prior radionuclide repeatability studies such as FDG and FLT.

10. MEASUREMENT OF EFFECT:

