1.3 Exploratory Objectives

- Disease assessment with ⁶⁸Ga-PSMA-HBED-CC PET/CT prior to and following investigational treatment
- To assess genomic DNA repair pathways in relationship to outcome following fractionated dose ¹⁷⁷Lu-PSMA-617
- To assess patient reported outcomes using FACT-P and the Brief Pain Inventory short form
- To assess the immune effect of ¹⁷⁷Lu-PSMA-617
- To assess the reproducibility of ⁶⁸Ga-PSMA-HBED-CC PET/CT

2. BACKGROUND:

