2.7.4 Immune assays

While there are only a selected number of prospectively performed studies of PSMA-targeted radionuclide therapy, it is clear that there are a subset that respond well for a durable period of time (i.e. “the tail of the curve”) and those that do not respond or have PSA declines for a short period of time. It has been proposed that radiation may generate immune responses with an abscopal response documented. As in most cases, PSMA-targeted radionuclide therapy successfully targets (by imaging) all known sites of disease, an abscopal response is difficult to document. However, sublethal doses of radiation may still well generate an immune response. We plan to study this effect with assays of immunogenic cell death and antigen spread. We will assess immunogenic cell death by assessing high mobility group box 1 (HMGB1) in serum and

calreticulin on CTCs. We will also collect serum and assay antigen spread by comparing pre-treatment to post-treatment with cancer-associated protein microarrays.

2.7.5 Molecular imaging:

While there is an increasingly large body of clinical data for PSMA PET imaging (above), reproducibility of imaging has not been well studied in a test—retest format.

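### The PET test-retest analysis checks lesion SUVs against ±30% without saying what the limit applies to, and gives no measurement-error estimate, interval or handling of several lesions per patient

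*Combined protocol and SAP*

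**What the plan says.** Section 1.3 lists the exploratory objective: "To assess the reproducibility of" 68Ga-PSMA-HBED-CC PET/CT. Section 2.7.5 gives the reason: "reproducibility of imaging has not been well studied in a test—retest format".

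The analysis is in Section 9.2. The scans are voluntary ("Consenting subjects will undergo an optional study involving two scans with" the tracer), with 6 hours to 2 days between injections. Then: "This cohort of patients will be analyzed to ensure that the peak standardized uptake values", listed as SUVmean, SUVmax and SUVpeak, "of the lesions in the same patient/lesion" "is within an acceptable range of repeatability (+/- 30" percent. The range is taken from other tracers: "as demonstrated by prior radionuclide repeatability studies such as FDG and FLT".

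No other section adds to this. Section 12 does not mention the test-retest cohort. Section 12.1 offers general descriptive statistics, or listings where numbers are small. The McNemar, paired t and Wilcoxon tests under Analysis of Efficacy in Section 10.8 are for comparing images before and after treatment.

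**The concern.** A repeatability study should deliver the size of the measurement error and how well it is known. Section 9.2 asks only whether values fall in a range, and it leaves open:

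- whether 30% applies to each lesion, to some share of lesions, or to a 95% limit for the cohort;
- which of the three SUV measures decides, and which lesions are measured;
- how lesions from the same patient are combined;
- how many patients are expected.

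The paired tests in Section 10.8 do not help, because they look for a shift in the mean. Two noisy but unbiased scans would show no shift.

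At stake is the gap that Section 2.7.5 sets out to close. Patients would be scanned twice, and the report could be a pass or a fail on the same data, depending on a rule chosen afterwards.

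**Working it through.** The plan states no sample size, CV, repeatability coefficient or interval for this cohort, so there is no figure to reproduce. The ±30% is a criterion. The inputs below are assumptions, except the 30% (Section 9.2) and the ceiling of 63 treated subjects (Protocol Summary).

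**1. What 30% would mean as a repeatability limit.** With within-lesion coefficient of variation CV and normal errors, the 95% repeatability coefficient is RC = 1.96 × √2 × CV = 2.77 × CV. Setting RC = 0.30 gives CV = 0.30 / 2.77 = 0.108.

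**2. If every lesion must pass.** At RC = 30% each lesion lies inside with probability 0.95. For independent lesions the chance that all do is 0.95^10 = 0.60, 0.95^20 = 0.36 and 0.95^40 = 0.13. Positive correlation within patients would raise these figures.

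**3. If a majority suffices.** P(lesion inside) = 2Φ(0.30 / (√2 × CV)) − 1.

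| CV | RC | Share inside ±30% |
|---|---|---|
| 10.8% | 30% | 95% |
| 15% | 42% | 84% |
| 20% | 55% | 71% |

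So an all-lesions rule often fails a tracer that is exactly at the benchmark, and a majority rule passes tracers well outside it.

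**4. Why an interval is needed.** Take one pair per patient, n degrees of freedom, and chi-square limits RC × √(n/χ²). For n = 10 the factors are 0.699 and 1.755. An observed RC of 25% then has a 95% CI of 25 × 0.699 = 17.5% to 25 × 1.755 = 43.9%. For an observed RC of 30%:

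| Pairs | 95% CI |
|---|---|
| 10 | 21.0% to 52.6% |
| 20 | 23.0% to 43.3% |
| 27 | 23.7% to 40.8% |
| 63 (accrual ceiling) | 25.6% to 36.3% |

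**5. Several lesions per patient.** The design effect is 1 + (m − 1) × ICC. With 10 patients, m = 5 lesions each and ICC 0.3 it is 1 + 4 × 0.3 = 2.2. The 50 lesions then carry the information of 50 / 2.2 = 22.7, and an interval that ignores clustering is too narrow by √2.2 = 1.48. For ICC 0.1 and 0.5 the factors are 1.18 and 1.73.

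**6. Symmetric percent limits.** SUV change is a ratio. A rise of 30% reversed is 1/1.30 − 1 = −23%, so a symmetric ±30% depends on which scan is the reference.

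**7. Which pairs count.** Table 8, footnote n, allows the repeat scan before treatment or 6 to 48 hours after it. Section 6.1.1 describes it only as before treatment. Section 9.2 caps the gap between injections at 2 days. Section 6.1.1 places the screening injection at least 1 week before 177Lu in one line and at least 2 days before in another. Even with the shorter interval, a post-treatment repeat paired with the screening scan comes at least 48 + 6 = 54 hours after it, outside the 2-day cap. Such a pair also straddles treatment.

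**The case against.** Section 9.2 does not say that every lesion must lie within 30%. It speaks of analysing a cohort against a range shown in earlier studies, which can be read as comparing this cohort's repeatability with a published limit. A reader might infer a strict lesion-by-lesion pass/fail rule, but the text does not state one. That objection stands, and the 0.60, 0.36 and 0.13 apply only under that reading, with independent lesions and 30% taken as a 95% coefficient.

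A reader might also infer that the plan treats lesions of one patient as independent. It is silent on clustering, which is an omission and not a stated assumption.

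The objective is exploratory, the scans are optional and Section 12.1 sets a descriptive approach. A listing of lesion differences would still be informative, so the inference that the objective cannot be served at all goes too far.

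Finally, the pre/post comparisons in Section 10.8 are group-level tests, and no SUV-based response threshold is defined. Those tests do not depend on a repeatability coefficient, so they are not undermined.

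What survives is that neither reading comes with an estimator, an interval or a way to combine lesions, and no other section supplies them.

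**Conclusion.** The point holds as a low-severity weakness in an exploratory analysis. As written, Section 9.2 can neither quantify the tracer's repeatability nor justify a statement that it is within 30%, because the meaning of the limit is open and no measurement-error estimate, interval or clustering method is given. The conclusion rests on the text. The sizes are illustrations that rest on assumed CVs, numbers of pairs, lesions per patient and ICCs, with normal errors. They show that the answer can turn on an unstated rule, and that with about 10 pairs an observed coefficient of 25% is compatible with a true value near 44%. DLT/MTD and the PSA endpoint are not touched.

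**What to change.** Replace the check in Section 9.2 with an estimate:

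- For SUVmean, SUVmax and SUVpeak separately, analyse log SUV in a mixed model with lesions nested in patients.
- Report the within-lesion CV and the repeatability coefficient as asymmetric percent limits.
- Give a 95% CI that respects clustering by patient. Use a model-based interval if there are few patients, since a bootstrap is fragile there, and a patient-level bootstrap otherwise.
- Show the estimate and CI descriptively against the 30% benchmark, not as a pass/fail test. This stays within the descriptive approach of Section 12.1.
- State which lesions are measured and the expected number of patients.
- Reconcile Table 8 footnote n, Section 6.1.1 and Section 9.2 on the timing of the repeat scan. Report any pair that straddles 177Lu treatment separately from the test-retest estimate.

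The cost is revised wording and slightly more analysis, with no additional scans. The downside is that in a small optional cohort the interval may not exclude values above 30%, so the report may be less favourable than a simple within-range statement.

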10.1 CTC count response

All subjects in this study will get blood samples drawn (at screening and EOS visit) for CTC enumeration by CellSearch methodology. Our primary analysis will assess those whose CTC counts drop to less than 5 or stay below 5 (responders) vs. those who remain at least 5 or above (non-responders) at EOS visit.

In addition, it appears that decreases in CTC counts with therapy are a favorable marker even if the count remains at least 5. We will also analyze % changes in CTC counts with at least 50% decline in CTC count from baseline considered a response at 12 weeks. Best response will also analyzed (% increase or best % decrease at any point will also be reported in a waterfall plot).

As reported in phase III studies of men with mCRPC, a favorable CTC count and LDH level at 12 weeks has been associated with overall survival. We will report the

proportion of subjects who have CTC count <5 and normal LDH at the initial scan (efficacy) visit time point.

Additional reports associate an undetectable CTC count at 12 weeks as prognostic. We will report the proportion of subjects who have an undetectable CTC count at the initial scan (efficacy) visit time point.

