Circulating tumor cell (CTC) counts via the CellSearch platform were demonstrated to be prognostic in men with advanced prostate cancer prior to systemic therapy and a “conversion” from an unfavorable count (≥ 5 CTCs/7.5 mL) was associated with a median similar to those starting with favorable counts, leading to clearance of this particular test by the FDA (de Bono, Scher et al. 2008). More recently, the combination of CellSearch CTC enumeration and serum LDH have been demonstrated to have prognostic value, meeting Prentice criteria for survival surrogacy in the setting of abiraterone/prednisone treatment in men with mCRPC previously treated with docetaxel (Scher, Heller et al. 2015)

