- c: Any subject with grade ≥ 2 neutropenia or thrombocytopenia at Treatment Visit 2 will initially not be eligible to receive the second ^{177}Lu -PSMA-617 injection. The dose will be held until the toxicity has resolved to grade 1 for a maximum of 2 weeks. If the toxicity has not resolved after 2 weeks, the dose will be discontinued.
- d: CMP (with direct bilirubin in subjects with known Gilbert's syndrome)
- e: CTC enumeration via CellSearch methodology may be obtained during screening or prior to Treatment Visit 1
- f: CTC collection for research purposes may be performed during screening or prior to Treatment Visit 1: two 2.3% sodium citrate "light blue top" tubes (5.4 mL whole blood)
- g: Cell-Free DNA BCT[®] may be obtained during screening or prior to Treatment Visit 1 and will be whole blood collection in a tube intended for collection, stabilization and transportation of cell-free plasma DNA. 10 mL tube will be used for collecting whole blood for research purposes
- h: Radiographic evaluation will include bone scan, CT/MRI of abdomen/pelvis, and Chest x-ray (CXR waived if CT/MRI includes chest). Following mandatory repeat imaging with Scan/Efficacy visit, continued repeat imaging is recommended approximately 12 weeks until radiographic progression as part of standard care.
- i: Planar/SPECT imaging one week after the ^{177}Lu -PSMA-617 1st dose infusion in all subjects. Optional imaging will be performed on consenting subjects between Treatment Visit 1 (Between D2-D4) or prior to Treatment Visit 2 (D15 ± 1).
- j: Survival assessment and relevant medical history to be collected until death
- k: Short-term follow up to be completed q4 weeks following the scan visit until 6 months from the 1st treatment visit. Subjects who are progression-free at 6 months will continue with q4-week labs and q12-week standard imaging per guidelines (as in h above).
- l: PRO = patient reported outcomes = BPI-SF and FACT-P; to be performed at time points specified during treatment phase, then q12 weeks (at imaging time points) during short-term follow up until radiographic progression
- m: serum for immune assays; 1 sample to be collected at any time during screening prior to Treatment Visit 1, then again during Scan/Efficacy visit

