6.1.1. Screening Visit

The following procedures must be completed no more than 1 month prior to enrollment and no more than 4 weeks following enrollment.

- Informed Consent
- Demographics
- Medical History
- Previous therapy
- Surgical report will include date and type of surgery +/- lymphadenectomy
- Radiotherapy report will include modality of therapy with prescribed dose and field and dates of therapy
- Previous systemic (hormonal, chemo, other) therapy – drugs, doses, dates of therapy
- Complete Physical Exam including height and weight
- Brief Pain Inventory
- Vital Signs
- ECOG Performance Status
- CBC with differential and platelet count
- CMP (with direct bilirubin with known Gilbert's syndrome)
- PSA
- Testosterone
- CTC count via CellSearch methodology (may be collected prior to treatment C1D1, do not need to repeat if has known result within 1 month of C1D1)
- CTC for Research (may be collected prior to treatment C1D1)
- Cell-Free DNA BCT® Research blood sample (may be collected prior to treatment C1D1)
- Immune research blood sample (may be collected prior to treatment C1D1)
- CT or MRI (abdomen-pelvis), up to 1 month prior to enrollment
- Bone scan, up to 1 month prior to enrollment
- Any confirmatory tests to assess equivocal results of bone scan should also be completed within a month of enrollment
- CXR, up to 1 month prior to enrollment (CXR waived if CT chest performed)
- Single intravenous dose of ^{68}Ga -PSMA-HBED-CC ($5\pm 2\text{mCi}$ or $185\pm 74\text{MBq}$) at least 1 week prior to ^{177}Lu -PSMA-617 infusion
- ^{68}Ga -PSMA-HBED-CC PET/CT scan to confirm the PSMA expression at the tumor site(s). PET/CT scans will be obtained 1 to 3 hours after the infusion of ^{68}Ga -PSMA-HBED-CC. Optional repeat ^{68}Ga -PSMA-HBED-CC injection and PET/CT prior to treatment in consenting subjects for research purposes.
- Archival tissue for PSMA expression and genomic studies to identify DNA

damage

Screening (except required ^{68}Ga -PSMA-HBED-CC PET/CT scan) and visit #1 may occur on the same day provided results are available, all entry criteria are met, and the subject is registered on the study prior to dosing. In this instance, duplicate procedures do not need to be performed. ^{68}Ga -PSMA-HBED-CC should occur at least 2 days prior to Treatment Visit #1.

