6.1.2.2 Imaging visit (Day 8 ±1)

- Planar/SPECT imaging
- Targeted Physical Examination with vital signs and weight
- Medical History
- Brief Pain Inventory, FACT-P
- ECOG Performance Status
- CBC with differential and platelet count
- CMP (with direct bilirubin with known Gilbert's syndrome)
- Adverse event evaluation
- Concomitant medications

¹⁷⁷Lu-PSMA-617 infusion (Treatment Visit 2 Day 15 ±1 day)

The following procedures must be completed on the day of treatment with ¹⁷⁷Lu-PSMA-617:

- Targeted Physical Examination with vital signs and weight
- Medical History
- Brief Pain Inventory, FACT-P
- ECOG Performance Status
- CBC with differential and platelet count
- CMP (with direct bilirubin with known Gilbert's syndrome)
- PSA
- LDH
- Single intravenous dose of ¹⁷⁷Lu-PSMA-617 (Dose based on the Cohort in which the subject is enrolled)
- Adverse event evaluation
- Concomitant medications
- Concomitant procedures
- Optional imaging will be performed on consenting subjects between Treatment Visit 1 (Between D1-D4) and/or prior to Treatment Visit #2 on (D15 ± 1)

6.1.2.2 Follow-up visits: Follow up Visit 1 (Day 22 ±3), Follow up Visit 2 (Day 29 ±3), Follow up Visit 4 (Day 57 ±3)

- Targeted Physical Examination with vital signs and weight
- Medical History
- Brief Pain Inventory, FACT-P
- ECOG Performance Status
- CBC with differential and platelet count
- CMP (with direct bilirubin with known Gilbert's syndrome)
- PSA (Follow up Visits 2 & 4)
- LDH (Follow up Visits 2 & 4)
- Adverse event evaluation
- Concomitant medications

6.1.2.3 Follow-up lab visits: Follow up Visit 3 (Day 43 ±3); Follow up Visit 5 (Day 71 ±3)

- CBC with differential and platelet count
- CMP (with direct bilirubin with known Gilbert's syndrome)

These visits may be performed with any licensed provider at any CLIA certified lab, provided that the results are available/provided to the Investigator within allowable windows.

6.1.3. Scan (initial efficacy) Evaluation Visit (Day 85 ± 7); note that these study procedures are not expected to occur on a single day)

The following procedures must be completed during the initial scan visit(s):

- Targeted Physical Examination with vital signs and weight
- Medical History
- Brief Pain Inventory, FACT-P
- ECOG Performance Status
- CBC with differential and platelet count
- CMP (with direct bilirubin with known Gilbert's syndrome)
- PSA
- LDH
- Testosterone
- CTC count via CellSearch methodology
- CTC for research

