10.4 Duration of CTC response

Duration of CTC response is defined from the first CTC count drop to <5 (or $\leq 50\%$ of baseline) to the time CTC count increases to ≥ 5 (or $\geq 25\%$ increase from nadir).

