Median bPFS, rPFS, and OS, including survival curves, will be estimated using Kaplan-Meier methodology. Greenwood's formula will be used to calculate 95% confidence intervals for the Kaplan-Meier estimates. Percent change in PSA from baseline will be described by mean/median and standard deviation/inter-quartile range, as appropriate, depending on the distribution of percent change from baseline. Modified RECIST response (i.e., CR, PR, and CR/PR proportions), CTC count response proportion, defined favorable LDH/CTC proportion, and associated 95% confidence intervals, will be estimated via binomial proportions.

All subjects will undergo baseline and subsequent ⁶⁸Ga-PSMA-HBED-CC PET/CT, and

those treated with ¹⁷⁷Lu-labeled products will undergo planar +/- SPECT imaging. We will analyze the data for associations with response to treatment as well as survival by chi-square tests/Fisher's exact tests and log-rank tests, respectively. For pre/post imaging comparisons, McNemar's chi-square test and paired t-tests/Wilcoxon signed-rank tests will be used, as appropriate. We plan to report data for each individual study as well as across the studies.

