12.5.2. Analysis of Secondary Endpoints

For PSA response, CTC response and Imaging response, descriptive analysis will be performed. For imaging response RECIST criteria with PCWG3 modifications will be applied. Biomarker and patient reported outcome data will be analyzed within this

study as well as across additional radiolabeled-PSMA studies.

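### Minor: the main CTC 'response' rate pools converters with patients who start and stay below 5, and CTC response duration has no scheduled count after Day 85

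*Combined protocol and SAP*

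**What the plan says.** Section 10.1 compares two groups at the end-of-study visit. The favourable group is "those whose CTC counts drop to less than 5 or stay below 5 (responders"; the other group is patients who remain at 5 or above. The same section adds percentage change in count, a decline of at least 50% at 12 weeks, a waterfall plot of best change, the share with a count below 5 and normal LDH, and the share with an undetectable count.

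The efficacy analysis in section 10.8 states that "CTC count response proportion, defined favorable LDH/CTC proportion, and associated 95% confidence intervals, will be estimated via binomial proportions". It gives no baseline strata. Section 12.5.2 sets the level of the analysis: "For PSA response, CTC response and Imaging response, descriptive analysis will be performed".

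The reason for the threshold is in section 2.7.2: conversion from an unfavourable count "was associated with a median similar to those starting with favorable counts".

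Section 10.4 adds a duration: "Duration of CTC response is defined from the first CTC count drop to <5" (or to half of baseline or less), ending when the count rises to 5 or more (or by at least 25% from nadir). On sampling, Table 8 note e says "CTC enumeration via CellSearch methodology may be obtained during screening or prior to Treatment Visit 1", and section 6.1.1 waives a repeat where a recent result exists ("do not need to repeat if has known result within 1 month of C1D1"). The Day 85 scan visit (section 6.1.3) lists "CTC count via CellSearch methodology".

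**The concern.** Two kinds of patient count as responders. One enters at 5 or more and falls below 5, which is a change on treatment. The other enters below 5 and stays there, which may need no treatment effect at all. When both are in the numerator and everyone is in the denominator, the rate moves with the baseline mix. Two cohorts with the same conversion rate can then report different 'response' rates, and a reader may take the proportion and its interval as an on-treatment effect.

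The duration definition raises a different problem. It needs a first drop and a later rise, so it needs at least two counts after baseline. If the schedule provides only one, the rule cannot be carried out.

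**Working it through.** The plan states no target rate, power or sample size for CTC response, so there is no figure to reproduce. The check has two parts.

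**1. Dependence on baseline mix**

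Let f be the share with baseline below 5, s the share of those who stay below 5, and c the conversion rate among patients with baseline of 5 or more.

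- Rate as written = f·s + (1 − f)·c.
- Rate as written minus conversion rate = f·(s − c).

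The documents give no baseline CTC split for this population. The nearest figure is in section 2.5: in the earlier fractionated antibody trial, 25 patients had counts, of whom 14 declined, 8 were stably favourable and 3 increased. Assume that the other 17 all started at 5 or more and that the 8 stayed below 5. With k conversions, and exact (Clopper-Pearson) 95% intervals:

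| k | As written, (8+k)/25 | Conversion, k/17 | Gap |
|---|---|---|---|
| 0 | 8/25 = 32% (15–54%) | 0/17 = 0% (0–20%) | 32 points |
| 7 | 15/25 = 60% (39–79%) | 7/17 = 41% (18–67%) | 19 points |
| 14 | 22/25 = 88% (69–97%) | 14/17 = 82% (57–96%) | 6 points |

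Sensitivity to mix and maintenance, at an assumed c = 40%:

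- s = 100%: f = 20% gives 0.20 + 0.80 × 0.40 = 52%; f = 50% gives 0.50 + 0.50 × 0.40 = 70%.
- s = 80%: f = 20% gives 0.16 + 0.32 = 48%; f = 50% gives 0.40 + 0.20 = 60%.

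The same 40% conversion rate is thus reported as 52% to 70% under full maintenance and as 48% to 60% under 80% maintenance.

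The other planned summaries do not recover c. Percentage change and the 50%-decline rate are relative to baseline, but they do not use the threshold of 5 and are not restricted to patients starting above it. The LDH combination and the undetectable rate are states at 12 weeks, with no baseline split.

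**2. Duration against the schedule**

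| Visit | CellSearch count scheduled? |
|---|---|
| Screening or before Treatment Visit 1 (Table 8 note e; section 6.1.1) | Yes, one baseline count |
| Day 85 ± 7 scan visit (section 6.1.3) | Yes |
| Short-term follow-up (section 6.1.4) | No; blood tests are CBC, CMP, PSA and LDH |
| Progression (section 6.1.5) | No |
| Long-term follow-up (section 6.1.6) | No |

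Section 10.1 itself names only screening and the end-of-study visit. A drop is first seen at Day 85, and no later scheduled count can show its end. For the same reason, the best change at any point in section 10.1 is simply the Day 85 value when only scheduled data are used.

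**The case against.** The strongest reply is that nothing is hidden. Section 10.1 says openly that staying below 5 counts, and section 2.7.2 gives a prognostic reason for treating a count below 5 as a favourable state. Section 1.2 names the objective as changes in CTC count together with the rate of favourable CTC count and LDH. The baseline-relative summaries are planned as well, and a patient already below 5 does not become a 50% decliner by staying there. All of this stands: the pooled figure is valid as a favourable-count rate. What remains is the label 'response' and the missing conversion rate.

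The illustration also has limits. It borrows from a different agent. A decline is not a conversion, and some of those who declined or increased may have started below 5. The gap shrinks as conversion rises or maintenance falls.

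On duration, the definition is not tied to any objective or listed endpoint, and no analysis in sections 10.8 or 12.5.2 uses it. Off-schedule counts might exist, since section 6.1.6 allows information from external providers, but none is planned.

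A reader might infer two further faults that the documents do not support.

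- *That a patient rising from below 5 to 5 or more is unclassified.* The wording is loose, but the estimate is a binomial proportion with a defined numerator, so such a patient is simply not a responder.
- *That missing Day 85 counts have no rule.* Section 12.7.2 limits evaluability for response to patients who complete treatment and at least 12 weeks of scheduled follow-up. That already covers many patients who leave early; only an isolated missed draw is left open.

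**Conclusion.** The point holds as a minor one. The main CTC proportion mixes on-treatment conversion with baseline status, by f·(s − c). In the borrowed 25-patient example this is 32 points with no conversions and 6 points with 14. Those sizes rest on the assumed 17 patients starting at 5 or more and on full maintenance among the 8; they do not predict this trial's result.

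The duration of CTC response cannot be estimated from scheduled data. That follows from the visit lists without any assumption beyond reading the end-of-study visit as the Day 85 scan visit.

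A reader might infer from section 10.1's description of this as the primary CTC analysis that a trial conclusion is at risk. It is not. The CTC endpoint is secondary and descriptive, and neither the MTD determination nor the two-stage PSA rule uses it. A reader might also expect distortion of the cross-study work in section 12.5.2, but that section lists CTC response apart from the biomarker data to be analysed across studies, so the documents do not establish that consequence.

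**What to change.** In sections 10.1 and 10.8, report separately:

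- conversion to below 5 among patients with baseline of 5 or more;
- maintenance below 5 among patients with baseline below 5.

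Give each with its denominator and an exact 95% interval. Keep the overall proportion below 5 at 12 weeks, labelled 'favourable count' rather than 'response'.

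Reconcile section 10.4 and the best-at-any-point wording in section 10.1 with the schedule. The simplest way is to delete the duration definition and state that best change is the Day 85 value.

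The cost is wording and one extra table from data already collected, plus less precision in each part. If the earlier study's split applied to 27 phase II patients, 27 × 17/25 = 18.4, or about 18, would start at 5 or more. Near 50%, the exact 95% interval is about 48 points wide at 9/18, against 39 at 13/27. The remaining 9 would give about 34 points at 9/9 and 65 at 5/9. Retaining the overall rate keeps the more precise figure available.
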